### **Quality Control**

**1. Treatment Fidelity:** Drs. [name] and [name] [with technical assistance [TA] for specific interventions] will train and supervise research staff to ensure protocol execution with dyads.

**2. Recruitment Screener:** Includes collection of basic demographic data and the outcome of recruitment effort so that we can keep an accurate account of referral patients who are ineligible and/or refuse to participate in the intervention. We include a standard question about (intimate partner violence) IPV in the screener to determine if this is a reason for refusal and/or influence the communication/behavior in the relationship over time. Participants who screen positively, will be provided with information and resources about IPV in the individual visit and referrals placed to the primary health provider for additional services.

**3. Surveys:** We have developed a survey to collect sexual and reproductive health history, perceived barriers to treatment, and self-efficacy data to be administered online during the study visit. This interview will be modified for this study, but will include: demographics, reproductive and sexual history (# partners, partner status (main versus casual), relationship status, coital frequency, prior STIs, condom use consistency, contraceptive use preferences for partner notification (e.g. female partner notification, case worker notification, email, text message), emotional response to diagnosis, access to medical care, access to technology (phone, internet, text), social provisions scale, and the short-form survey instrument (SF-12) as a measure of health-related quality of life, Fertility Knowledge and Awareness Scale, clinical symptoms, sensation seeking scale, relationship qualities scale and intimate disclosure scales to measure relationship quality and dyad communication, childbearing motivation and communal coping. We will also query patients at the end of the intervention to determine their level of confidence for negotiating with their partner and their satisfaction with the experience. It is important to test these measures with participants and the timing of completion.

Participants will be contacted in 6-8 weeks for a brief (~30 min) telephone (or in-person) follow-up interview to assess sexual risk-taking behaviors, relationship status, social support, and satisfaction with the intervention experience.

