### 1. Abstract

Adolescents and young adults less than 25 years of age continue to have the highest rates of sexually transmitted infections [STIs] in the United States. While public health control programs have shown some success the disparities for this population remain. For this reason additional supports to increase engagement in care and reduction in acquisition of STIs as a part of establishing a healthy sexuality are needed. STI prevention work with adolescents has primarily targeted individual level factors and fails to address higher level factors such as peer, media, and relationship influences that may influence sexual decision-making and behavior. Partner notification and treatment is a key strategy for disease control within the population to improve the health and well-being of the individuals affected by the disease process and has previously been explored among adults for STI/HIV prevention work but has yet to be explored in adolescents and young adults. In our prior research, we demonstrated that adolescent girls with complicated sexually transmitted infections are highly likely to notify their partners for treatment (88-92%), but that only those who experience brief behavioral interventions are 3 times more likely to be successful in arranging for partner treatment than girls receiving standard of care. There has been a failure to use our knowledge about the structure and function of romantic relationships occurring during critical developmental learning periods, to engage youth for individual and dyadic behavior change. Partner interventions for STI prevention have significant promise for harnessing the power of relationship dynamics to enhance sexual decision-making, communication, and subsequent health behaviors. In the EXPERIENCE study, we propose to pilot an intervention designed to change STI outcomes by understanding partners and the learning environment related to sex. If successful, this pilot will support adoption of an alternative cost conscious, but effective strategy for engaging young men involved in sexual relationships affected by an STI diagnosis for both individual and relationship behavior change. Proving that heterosexual adolescents and young adults can consistently and safely engage their partners in a supportive outpatient setting that integrates treatment with evidence-based STI/HIV prevention interventions delivered by gender matched professional dyads.

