We will provide text message boosters related to care-seeking behavior, condom use, and condom access, over the six weeks of the study. Messages will be standardized and delivered via an automated one-way system. These messages have well tested in the field with urban adolescents and young adults. No protected health information is disclosed as a part of this communication, but youth will be encouraged to provide an extra layer of protection on existing cell phone security to allow for an additional degree of privacy related to message content. We will send a welcome message right after enrollment “welcome to the EXPERIENCE study”, followed by one text every week, including: “don’t forget to try out your new communication skills”, “Did you practice the *Experience* role play? Text the # of times you practiced together”, “Condoms prevent STDs. Stop by the clinic if you need some”, “Condoms can improve pleasure, if you need some stop by the clinic”, and “Want to up your game, practice your condom technique”. In week six, we will send “Thanks for trying EXPERIENCE, we’ll call you soon for feedback”.

We will use SMS services through TextNow for communicating with participants in both arms of the study. TextNow is one of the fastest growing technology companies in North America and has created an all IP, cloud-based mobile phone carrier and mobile messaging and application service that has more than 8 million monthly active users. It is the hybridization of Wi-Fi with cellular for texting and calling and can be enabled for use on a phone, tablet, or computer that makes this platform optimal for our pilot study. Further, TextNow has strict policies to protect the user to prevent unauthorized disclosure of information and physical, electronic, and procedural safeguards are in place according to industry standard procedures and security procedures. Research staff will be responsible for monitoring and using the online account to send standardized text-message boosters to participants in the study. Since a telephone number is created with each account, the telephone number will be recognizable to participants as EXPERIENCE communication. Finally, all participants will be encouraged to use standard safety mechanisms such as a pin or password to lock access to their cell phones by others.

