## 8. Risks

- a. Medical risks, listing all procedures, their major and minor risks and expected frequency.

There are no significant medical risks involved in this study. Sexual history interviews and collection of vaginal and urine specimens are a part of routine care. While the study will attempt to preserve patient confidentiality, there is potential for breaches of confidentiality, but minuscule

given the limited number of personnel with access to participant information. Disclosures by the partner to others are an ongoing risk dictated by public health practice given the CDC recommendations for partner notification and treatment. Non-enrolled patients will be given the option to notify partners anonymously for treatment and study participation using standard issue notification cards commonly employed through the health department. Finally, while the EXPERIENCE intervention focuses on positive communication and condom negotiation; dyad strife may develop during the context of the joint session. While health educator will be trained in basic conflict resolution; there are staff onsite to provide both mental health [social work; mental health counselors, psychologists] and seasoned security staff available to intervene as needed. We have previously followed AYA and their partners as a part of clinical practice and in research trials [clinic and community-based] without complaints of undue exposure, confidentiality breach, or adverse event such as physical or emotional harm to a patient, family member, and/or sexual partners who have presented for STI treatment. There have also been no complaints by patient, parents/guardians about AYA participation in the sexual health research studies. Further, this project was presented to the community advisory board (CAB) for the Harriet Lane Clinical Program (Home of the Adolescent Young Adult Practice) [Meeting December 18, 2014] and community youth and parents found the project highly relevant and were overwhelmingly support or this research strategy. Input on youth engagement and retention from CAB members has been incorporated alongside preliminary data and research expertise to optimize our approach and to minimize risk.

There are no additional risks associated with these telephone calls as this is in line with the work that we are currently doing in this study.

b. Steps taken to minimize the risks.

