Disease Control and Prevention/Johns Hopkins Medicine), [name] (Professor of Pediatric, Johns Hopkins Medicine, and [name], MD, MPH (Adolescent Medicine, Harvard Medical School) The DSMC will develop a charter to govern DSMC activities and develop a communication plan with the research team. Annual data reports will be submitted to the DSMC for review prior to the annual continuing IRB review as a part of ongoing study and subject monitoring. Online tracking of patient data will be managed via the clinical research monitoring system (CRMS) and Biostatistical consultation and support will be obtained through the Johns Hopkins Biostatistics Center in conjunction with the Johns Hopkins Institute for Clinical and Translational Research. [name] has budgeted for and will submit a consultation request upon grant approval. [name] has effectively utilized this service for prior research. Use of this service for data analytic support will also allow for the study to remain single blinded to the principal investigator.

c. Plan for reporting unanticipated problems or study deviations.

Any unanticipated problems or adverse events will be reported to the IRB immediately. Deviations from the original study protocol will be requested through a change in research request.

d. Legal risks such as the risks that would be associated with breach of confidentiality.

There are no anticipated legal risks associated with study participation. We have been following girls in the community for many years and in their homes without consequence as we have put safeguards in place to protect confidentiality as outlined above.

e. Financial risks to the participants.

There are no anticipated financial risks to participations that are unaccounted for in the support and remuneration plan.

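### After the recruitment screener, no listed trial contact asks about partner violence or conflict and no safety outcome is defined, so the pilot cannot support its wording on safe engagement

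*Combined protocol and SAP*

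**What the plan says.** - **Intended conclusion.** Section 1 (Abstract): "Proving that heterosexual adolescents and young adults can consistently and safely engage their partners in a supportive outpatient setting".
- **Named risk.** Section 8a: "dyad strife may develop during the context of the joint session". The safeguards described are educators trained in conflict resolution, with mental health and security staff on site.
- **IPV at entry.** Section 4, Quality Control, item 2: "We include a standard question about (intimate partner violence) IPV in the screener to determine if this is a reason for refusal and/or influence the". The sentence goes on to the couple's communication and behaviour over time. Section 5 excludes dyads with evidence of IPV.
- **Contacts after the screener.** Quality Control, item 3, lists a study-visit survey that includes relationship-quality and disclosure scales. It then lists an end-of-intervention query on negotiation confidence and satisfaction, and a 6-8 week "follow-up interview to assess sexual risk-taking behaviors, relationship status, social support, and satisfaction with the intervention experience".
- **After the session.** EXPERIENCE Intervention: "We will provide text message boosters related to care-seeking behavior, condom use, and condom access, over the six weeks of the study". Control dyads receive general-health texts and no joint session.
- **Outcomes.** Section 7 defines feasibility (recruitment and retention) and acceptability (satisfaction). It defines no safety outcome.
- **Oversight.** Section 8: "Annual data reports will be submitted to the DSMC for review". The content of those reports is not specified. Adverse events go to the IRB immediately.

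**The concern.** The one question about violence is asked before anyone is exposed to the intervention, and a dyad with evidence of IPV does not enter. The answer therefore says nothing about what happens after the joint session. Item 2 of Quality Control wants the question to inform on the relationship over time, but no repeat is listed, so the plan does not meet its own purpose.

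Two things are at stake. The first is participant protection: a named risk has no planned enquiry once the couple has left the visit. The second is interpretation: the trial randomises dyads to a joint session or none, which is the right design for seeing whether that session provokes conflict, but the listed data would not show it. A change in relationship status at 6-8 weeks cannot separate harm from an ordinary break-up.

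**Working it through.** The documents give no safety rate, threshold or power figure, so there is nothing to reproduce. The check has two parts.

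**1. What each route can detect**

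| Route | Where | Listed content | Solicits IPV or conflict after exposure? |
|---|---|---|---|
| Recruitment screener | Quality Control, 2 | IPV question | No, it precedes exposure |
| Study-visit survey | Quality Control, 3 | Relationship-quality and disclosure scales among others | Not listed; items not shown |
| End-of-intervention query | Quality Control, 3 | Confidence, satisfaction | Not listed |
| 6-8 week interview | Quality Control, 3 | Four topics | Not listed |
| In-depth interview | In-depth Interviews | Relationship qualities, communication | Optional subset; not by name |
| Educators; 20 recorded sessions | EXPERIENCE Intervention; Section 5 | Observation, fidelity, themes | In session only |
| Adverse event and abuse reporting | Section 8 | Events and disclosures that come to notice | Unsolicited |
| COVID-19 calls | Section 1 | Perceived safety | Described for another cohort (Tech2Check) |

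No row gives solicited, systematic ascertainment in both arms after the session.

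**2. What a count of zero could mean**

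Inputs: 50 dyads planned, with a target of 40 complete (Section 4, Participants and Recruitment). Assumptions: 1:1 allocation, which is not stated, giving 20 to 25 intervention dyads; the 40 at which recruitment stops is read as dyads; all intervention dyads are assessed. Fewer dyads would widen every bound.

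One-sided 95% upper bound with zero events = 1 − 0.05^(1/n):
- n = 20: 1 − 0.05^(1/20) = 0.139
- n = 25: 1 − 0.05^(1/25) = 0.113

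If only a fraction s of events is reported, zero reports bound the true rate at that value divided by s. The chance of at least one report at true rate p is 1 − (1 − ps)^n. The documents give neither s nor p; the values below are illustrative, with p = 5%.

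| s | Upper bound, n = 20 | Upper bound, n = 25 | Chance of ≥1 report, n = 20 | Chance of ≥1 report, n = 25 |
|---|---|---|---|---|
| 1 | 13.9% | 11.3% | 64% | 72% |
| 0.5 | 27.8% | 22.6% | 40% | 47% |
| 0.25 | 55.6% | 45.2% | 22% | 27% |

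Under the listed plan s is unknown for harm after the session, so no bound could be stated for it. The first row is the most that complete collection could deliver, and it is still wide.

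**The case against.** The strongest reply is that the plan is not blind to harm. The named risk is strife during the joint session. Both health educators attend that session and 20 sessions are recorded. Adverse events go to the IRB, and suspected abuse disclosed in counselling must be reported. This stands for events inside the session. It does not reach what happens at home afterwards.

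A reader might infer more than the documents support:

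- *That the questionnaires contain no relevant item.* Only topic lists are shown, the survey is to be modified for this study, and the scale items are not visible. The point is limited to listed topics.
- *That partner violence is a stated risk of the intervention.* Section 8 names dyad strife. IPV is a screening item and an exclusion.
- *That harm is recorded only if a participant volunteers it.* Staff observation is a separate route.
- *That the DSMC will see no harm data.* The content of its reports is unspecified and its charter is still to be written.
- *That the weekly texts amount to six weeks of role play at home.* Of the five messages listed between the welcome and the closing text, one concerns communication skills and one the role play. The other three concern condoms.

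Two further objections have weight. The Abstract's sentence is aspirational, and no objective or outcome claims safety, so rewording it cures the overclaim. It does not cure the gap in collection. Asking about violence by telephone also raises privacy, mandated-reporting and referral issues, since participants may be 16 or 17 and the existing provisions are framed around the screener, the counselling sessions and registered clinic patients. That adds to the fix and does not defeat it: under COVID-19 Procedures, screening is already done by telephone.

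**Conclusion.** The point holds in limited form. No listed topic after the recruitment screener solicits IPV or partner conflict, and Section 7 has no safety outcome. Harm arising after the joint session would surface only through unsolicited reports or the optional in-depth interviews, so an empty record would be uninformative.

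The bounds of 13.9% (20 dyads) and 11.3% (25 dyads) describe the size of the pilot under assumed 1:1 allocation and full ascertainment. They do not measure the defect. They show that added questions would make harm countable and comparable between arms, but would not prove safety. The change should be made because it protects participants and makes use of the randomised comparison. It does not affect the feasibility or acceptability outcomes.

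**What to change.** 1. **Section 4, Quality Control, item 3.** In the 6-8 week interview, repeat the screener's IPV question and add one item on conflict, fear or pressure from the partner since the visit. Add one item on distress or conflict to the exit survey. Use the same items in both arms and ask each partner separately.
2. **Privacy and handling.** Before these items, check that the participant can speak privately. This matters for telephone follow-up and for exit surveys read aloud by recruiters in the virtual procedures. Extend the existing referral and mandated-reporting provisions (Quality Control, Section 5, Section 8b) explicitly to these contacts and to partners who are not registered clinic patients.
3. **Section 7.** List these responses as a descriptive outcome, counted per dyad and by arm, with exact confidence intervals and the number of dyads assessed.
4. **Section 8, Data Safety Monitoring Plan.** State that the DSMC report includes these counts by arm.
5. **Section 1.** Reword the sentence on safe engagement so that it claims no more than the interval will support.

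The cost is two or three items in contacts already planned (an exit survey and a call of about 30 minutes), a few minutes per contact and a change-in-research request. Some positive answers will need referral or reporting.

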## 5. Inclusion/Exclusion Criteria

**Inclusion Criteria:** The index patient must be 16-25 years, engage in male-female [heterosexual] intercourse, permanently reside in the Greater Baltimore Metropolitan Area (includes surrounding counties, i.e. Baltimore County, Anne Arundel, Howard County), willing to recruit their main sexual partner for the study, are willing to participate in a single individual session with a health educator followed by a joint debriefing session together with both health educators. The partner must be 16-30 years, engage in male-female [heterosexual] intercourse, , permanently reside in the Greater Baltimore Metropolitan Area (includes surrounding counties, i.e. Baltimore County, Anne Arundel, Howard County), willing to recruit their main sexual partner for the study, are willing to participate in a single individual session with a health educator followed by a joint debriefing session together with both health educators.

**Exclusion Criteria:** Index participants and partners who are unable to communicate with staff or participate in study procedures due to cognitive, mental, or language difficulties, will not be eligible for recruitment into the study. Dyads will also be excluded if in same-sex main partnership or a member of the dyad is currently enrolled in another sexual behavior study, the patient/partner is currently pregnant, one or both partners has a known concurrent HIV infection, one or more partners has a pending incarceration, there is more than five years age difference between the two partners, or there is evidence of intimate partner violence [IPV] in the relationship. Couples who are married, engaged or in a committed relationship greater than two years will be excluded. Individuals who screen positive for IPV will be referred to local resources for assistance. The Title X Clinic has adopted the RADAR screening approach with identified social work services in place for registered clinic patients who need further assessment and assistance.

## 6. Drugs/ Substances/ Devices

- a. The rationale for choosing the drug and dose or for choosing the device to be used. N/A
- b. Justification and safety information if FDA approved drugs will be administered for non-FDA approved indications or if doses or routes of administration or participant populations are changed. N/A
- c. Justification and safety information if non-FDA approved drugs without an IND will be administered. N/A

## 7. Study Statistics

- a. Primary outcome variable. The primary outcome variable for this pilot study is feasibility of recruitment. Recruitment feasibility will be defined as the number of dyads completing the intervention out of number of eligible dyads. The feasibility of short-term retention will be calculated as the proportion of enrolled participants, who complete a follow-up interview at 6 weeks.
- b. Secondary outcome variables. The secondary outcome variable for this pilot study is acceptability, measured as participant satisfaction with their intervention experience. Participant satisfaction will be measured using a brief survey asking participants to rate their experience and qualitative feedback documented.
- c. Statistical plan including sample size justification and interim data analysis.

We will enroll a total of 50 adolescent dyads. While the choice of 50 dyads is inherently arbitrary, it is the number we feel we can realistically enroll within our limited time of this pilot study. While we won't have power to detect statistically significant differences, we will be able to examine correlations, which will be informative for future research proposals. To address each aim, we will evaluate our outcomes, feasibility and acceptability, against benchmarks from previous studies. To address aim 1, we will compare observed recruitment rates from the proposed pilot study to expected recruitment rates. Expected recruitment rates will be determined from previous studies that recruited adolescents with an STI diagnosis. Prior studies recruiting from the Adolescent Medicine Clinic have achieved recruitment rates ranging from 48 to 91%. To address aim 2, we will use a similar approach, comparing satisfaction scores to an a priori benchmark of patient satisfaction. Based on previous work, average patient satisfaction greater than 80% would be necessary to conclude that the intervention is acceptable.

For the in-depth interviews, audiotapes and notes from the sessions will be transcribed verbatim and uploaded to NVivo 11, a qualitative data analysis software package. We will use constant comparative method of grounded theory to analyze the qualitative data. Using a 3-stage analytic coding strategy, the transcripts will be examined for salient categories (codes) through constant comparison between text within a single interview, within dyads, and between interviews. Axial coding will be completed to identify relationships between the codes. Finally, through selective coding the core category will be identified and a theory will be developed that integrates and explains relationships between axial codes. To ensure validity and qualitative rigor, we will use the following three strategies: audit trail with external review, deviant case analysis, and peer debriefing. Additionally, to ensure reliability in coding, two coders will independently code each transcript and through regular meetings will compare and discuss application of the codebook to each transcript until they reach consensus.

